#### **10.2.2. Modified Intent-to-Treat Population**

The Modified Intent-to-Treat Population (mITT) will consist of all subjects who are transplanted. The mITT analyses will be considered secondary analyses of effectiveness. The safety analysis will also be based on the mITT population.

#### **10.2.3. Donor Liver Population**

The Donor Liver Population will consist of all donor livers which have preservation initiated using the OCS Liver System.

## **10.3. Data Analysis**

The statistical analysis plan (SAP) will provide details on the statistical methods planned for this study and will be finalized prior to the database lock. Statistical summaries described in the sections below will primarily be provided for all subjects (i.e., overall summary) in the analysis populations of interest unless otherwise stated.

### **10.3.1. Subject Disposition**

Subject disposition will be summarized and presented for the number and percentage of subjects who were enrolled, screen failures, completed the study, and discontinued early (including reasons for discontinuations).

### **10.3.2. Major Protocol Deviations**

Major protocol deviations will be identified and documented based on a review of potential deviations. The potential major protocol deviations will be identified before database lock, either through programmatic checks of study data (e.g., inclusion/exclusion criteria violations), as well as through review of selected data listings (e.g., site-entered comments). The potential major protocol deviations to be reviewed include, but are not limited to, subjects who did not meet inclusion/exclusion criteria or eligibility was not adequately verified.

Individual major protocol deviations will be presented in a data listing. The number and percentage of subjects with major protocol deviations will be summarized by the type of deviations.

### **10.3.3. Demographics and Baseline Characteristics**

Demographics, including (age, gender, race, and ethnicity where applicable), and other baseline characteristics collected at screening, such as height, weight, body mass index will be summarized using descriptive statistics. These data will be presented as a listing.

### **10.3.4. Primary Effectiveness Endpoint**

The primary effectiveness endpoint for this study is the incidence of Early Liver Allograft Dysfunction (EAD) or primary non-function, defined as presentation of one or more of the following criteria:

- AST level > 2000 IU/ml within the first 7 postoperative days;
- Bilirubin  $\geq$  10 mg/dl on postoperative day 7;
- INR  $\geq$  1.6 on postoperative day 7; or
- Primary non-functioning graft within the first 7 days.

This endpoint will be analyzed using the Per Protocol and mITT Populations. The Per Protocol analysis will be considered the primary analysis.

Subgroup analyses of the primary effectiveness endpoint will be performed for the following subgroups of patients:

- DCD (donation after circulatory death) patients
- Fatty liver patients
- Donor Age
- Recipient with MELD  $>$  30.

No data imputation or statistical tests will be performed for these subgroup analyses.

### 10.3.5. Secondary Effectiveness and OCS Donor Liver Assessment Endpoints

The secondary effectiveness endpoints for this trial are as follows:

- OCS donor liver assessment during perfusion, defined as, among donor livers preserved using OCS for the entire preservation period, the proportion of livers on which measurements of all of the following during perfusion will be available on OCS device before transplant
  - Lactate level (every two hours)
  - Average bile production rate (based on total bile production volume and duration of OCS perfusion)
  - Hepatic artery pressure (continuously)
  - Portal vein pressure (continuously)
- OCS Measurements during organ perfusion
- Patient survival at Day-30 post-transplantation
- Patient survival at time of initial hospital discharge post-transplantation.

These endpoints will be analyzed using the Per Protocol and mITT Populations, with the Per Protocol analysis being considered the primary analysis. Multiple imputation methods will be used for data imputation for patients with missing values for these endpoints.

Subgroup analyses of the secondary endpoints will be performed for the same subgroups of patients as for the primary effectiveness endpoint. No data imputation or statistical tests will be performed for these subgroup analyses.

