## 5.2. Secondary Effectiveness and OCS Donor Liver Assessment Endpoints

- OCS donor liver assessment during perfusion, defined as, among donor livers preserved using OCS for the entire preservation period, the proportion of livers on which measurements of all of the following during perfusion will be available on OCS device before transplant:
  - Lactate level (every two hours)
  - Average bile production rate (based on total bile production volume and duration of OCS perfusion)
  - Hepatic artery pressure (continuously)
  - Portal vein pressure (continuously)
- Patient survival at Day 30 post-transplantation
- Patient survival at initial hospital discharge post liver transplantation.

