## 7. PRE-OPERATIVE TRIAL PROCEDURES

### 7.1. Subject Identification

All patients on the liver transplant waiting list who are being treated by trial investigators will be identified. Those patients who initially appear eligible for the trial will have the trial thoroughly explained to them, be invited to participate, and will be asked to sign an informed consent for participation in the trial prior to treatment. When a matching donor liver becomes available, the inclusion and exclusion criteria will be re-verified. When a final decision is made to transplant the liver, the recipient will be assigned a subject identification number.

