## 7.5. **Donor Liver Acceptance for Transplantation following OCS Liver Preservation**

All donor livers that are preserved on the OCS Liver System are expected to be transplanted into a matching consented recipient. Any decision to turn down livers after they have been retrieved and preserved on OCS Liver System should be done with notification to the Site PI and the donor liver examined by the transplant center's qualified liver transplant pathologist and/or tissue slides/samples to be sent to core lab for the study for further examination. All reasons for turning down a donor liver after it has been preserved on the OCS Liver System will be collected in the eCRFs.

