### **10.2. Analysis Populations**

#### **10.2.1. Per Protocol Population**

The Per Protocol (PP) Population will consist of all subjects who are transplanted and have no major protocol violations and for whom the donor liver received the complete preservation procedure. The major protocol violations that will exclude a subject from this population are the following:

- Ineligible for the study according to the recipient inclusion and exclusion criteria
- Ineligible for the study according to the donor organ inclusion and exclusion criteria
- Failure to complete adequate post-transplant assessments to support the primary, secondary or safety endpoints
- Other major protocol violations.

The primary analysis of effectiveness and of secondary and other endpoints will be based on the PP Population.

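### The OCS donor liver assessment endpoint is defined per preserved liver but analysed only in transplanted subjects, so livers fully preserved and then declined drop out

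*Combined protocol and SAP*

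**What the plan says.** The Synopsis, Section 5.2 and Section 10.3.5 define the endpoint in the same way. The unit is the liver and the denominator is "among donor livers preserved using OCS for the entire preservation period". The outcome is "the proportion of livers on which measurements of all of the following during perfusion will be available on OCS device before transplant". The four required items are lactate, average bile production rate, hepatic artery pressure and portal vein pressure.

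Section 10.3.5 sets the analysis populations for all secondary endpoints together: "These endpoints will be analyzed using the Per Protocol and mITT Populations, with the Per Protocol analysis being considered the primary analysis". The Synopsis (Effectiveness Analysis) says the same. Per protocol (Section 10.2.1) requires transplantation, no major violation and a complete preservation procedure. One listed violation is "Failure to complete adequate post-transplant assessments to support the primary, secondary or safety endpoints". The mITT population (Section 10.2.2) "will consist of all subjects who are transplanted".

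A third set, the Donor Liver Population (Section 10.2.3), covers every liver on which OCS preservation was started. Section 10.4 names it only for device failure.

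The plan foresees livers that are preserved and then not used. Section 7.5 states: "All reasons for turning down a donor liver after it has been preserved on the OCS Liver System will be collected in the eCRFs". Section 11.1 lists turn-down after OCS preservation as a possibility, and Section 10.4 summarises the reasons for non-transplantation.

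**The concern.** The endpoint definition and the analysis sets describe different groups. A liver kept on OCS for the whole preservation period and then declined belongs in the denominator as written, yet no planned analysis reports whether its measurements were available. Section 10.4 gives the reasons for non-use and device failures, which is a different question.

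The trial objective covers assessing donor livers as well as preserving them. Section 11.2 bases acceptance after OCS partly on perfusion markers and partly on conventional clinical standards. Whether a liver is transplanted is therefore partly a consequence of the assessment this endpoint describes, and conditioning on transplantation removes part of the group in question.

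The per protocol exclusion for inadequate post-transplant assessments adds a smaller distortion. It can remove a liver for something that happened after perfusion ended. The mITT set restores such livers but not the declined ones.

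**Working it through.** **Which livers enter which set**

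| Liver | Meets the Section 5.2 denominator | Per protocol | mITT | Donor Liver Population |
|---|---|---|---|---|
| Full OCS preservation, transplanted, no major violation | yes | yes | yes | yes |
| Full OCS preservation, transplanted, recipient's post-transplant assessments inadequate | yes | no | yes | yes |
| Full OCS preservation, turned down | yes | no | no | yes |
| OCS started, not completed, turned down | no | no | no | yes |

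No defined set matches the denominator exactly. The subset of the Donor Liver Population that completed OCS preservation does.

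**Inputs for an illustration.** The plan states no expected value for this endpoint, so there is no figure to reproduce. Only 184, the maximum number of transplanted recipients (Section 10.5), comes from the documents. The following are assumptions:
- All 184 transplanted livers completed OCS preservation.
- 175 of the 184 have all four measurements.
- The number of fully preserved but declined livers is t = 5 or 10.
- Between none and all of the declined livers have all four measurements.

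**Formula.** With a of the t declined livers complete, the proportion is (175 + a)/(184 + t). The shift from the transplanted-only figure is t/(184 + t) × (availability in declined livers − availability in transplanted livers).

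**Results**, with exact 95% intervals:
- Transplanted only: 175/184 = 95.1% (90.9 to 97.7).
- t = 5, weight 5/189 = 2.6%: 175/189 = 92.6% (87.9 to 95.9) if none is complete; 180/189 = 95.2% (91.2 to 97.8) if all are.
- t = 10, weight 10/194 = 5.2%: 175/194 = 90.2% (85.1 to 94.0) if none is complete; 185/194 = 95.4% (91.4 to 97.9) if all are.
- t = 0, or equal availability in the two groups: no shift.

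**Per protocol exclusion.** Suppose 5 of the 184 livers are dropped for post-transplant reasons. If all 5 had complete measurements, the figure is 170/179 = 95.0%. If none did, it is 175/179 = 97.8%.

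**The case against.** *The definition may already mean transplanted livers.* It asks for measurements available ahead of transplant, and someone could read that as limiting the endpoint to livers that were transplanted. The phrase says when the measurements must be available; the clause that sets the denominator has no such limit. If the limit is intended, the definition has to state it.

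*There may be few or no such livers.* Section 7.5 opens by expecting every OCS-preserved liver to be transplanted. That points to a small number, and the plan gives no count. Section 11.1 calls the anticipated frequency known but does not state it. This limits the likely size of the effect. It does not remove the conflict, because the same section provides for turn-downs.

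*Declined livers may well have complete data.* This objection has force. The endpoint asks whether measurements exist, not whether they are good, and a liver declined on its perfusion markers would usually have had those markers measured. A reader might infer that the planned analysis must overstate availability. The documents do not support that; the low ends above are worst cases.

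*Imputation.* Section 10.3.5 adds: "Multiple imputation methods will be used for data imputation for patients with missing values for these endpoints". A reader might infer that unavailable measurements could be imputed into successes, or that the Synopsis, Section 10.3.4 and Section 10.3.5 contradict each other. Neither inference is secure. In the ordinary reading an unavailable measurement is an observed failure, so there is nothing to impute. The Synopsis gives imputation for the primary endpoint, Section 10.3.4 is silent for its main analysis, and Section 10.3.5 gives it for the secondary endpoints. These are silences, and the SAP still to be finalised (Section 10.6) can settle them.

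**Conclusion.** The stated analysis sets conflict with the endpoint's own denominator. Livers fully preserved on OCS and then declined qualify for the endpoint and are in neither per protocol nor mITT. Per protocol can also drop livers for reasons unrelated to perfusion.

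The size and direction of the effect cannot be determined from the documents. Under the assumptions above, including 5 to 10 declined livers changes 95.1% by −2.5 to +0.1 points (t = 5) or −4.9 to +0.3 points (t = 10). The downward limits require that no declined liver has complete measurements.

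The endpoint is secondary and descriptive, with no hypothesis test. A reader might infer that the primary effectiveness result is affected too. It is not: that endpoint is observed in recipients, so transplanted sets suit it. The safety analysis and the stopping rule are also untouched. The point is worth correcting because the text contradicts itself and the correction is small.

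**What to change.** For this endpoint only, amend the Synopsis and Section 10.3.5, and carry the change into the SAP:

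1. Make the main analysis set all Donor Liver Population livers on OCS for the whole preservation period, transplanted or not. Keep per protocol and mITT as supportive.
2. Report beside the result the number of livers that completed OCS preservation and were then turned down.
3. State that a liver lacking any of the four required measurements counts as not available, and that imputation does not apply to this endpoint.

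The cost is wording plus one data check. The Donor Liver Population is already defined, and the donor schedule in Appendix 2 already lists OCS preservation parameters, lactate levels and non-transplant reasons. The check concerns lactate, which Section 7.4 has measured on a standard blood analyzer. Section 7.1 says: "When a final decision is made to transplant the liver, the recipient will be assigned a subject identification number". A declined liver may therefore have no subject number, and the sponsor should confirm that its lactate values are entered under the donor identification number recorded in Section 7.3. The sponsor should also accept that the reported figure may be less favourable.

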### 10.4. Analysis of Safety

Safety will be analyzed principally by examination of the frequency of liver graft-related serious adverse events (SAEs) up to the 30-day follow-up after transplantation. This endpoint is defined as the average number of liver graft-related serious adverse events through the 30 days post-liver transplantation per subject, consisting of the following serious adverse events (at most one per type per person):

- Primary non-function (defined as irreversible graft dysfunction requiring emergency liver re-transplantation or death within the first 10 days, in the absence of immunologic or surgical causes)
- Ischemic biliary complications (ischemic biliary strictures, and non-anastomotic bile duct leaks)
- Vascular complications (liver graft-related coagulopathy, hepatic artery stenosis, hepatic artery thrombosis and portal vein thrombosis)
- Liver allograft infections (liver abscess, cholangitis, etc.).

In addition, the numbers and percentages of subjects experiencing at least one liver graft-related AE, at least one (definitely or probably-related) device-related AE, at least one unanticipated AE, and at least one serious AE, and the number and percentage of deaths will all

be tabulated. Also, the number of liver graft-related adverse events and the number and percentage of subjects experiencing liver graft-related adverse events will be tabulated by system organ class and preferred term using MedDRA. A similar analysis will be performed for LGRSAEs. AEs will also be tabulated at the event level by system organ class and preferred term and the relationship of the adverse event to the device using counts and percentages. Similar analyses will be performed by the severity of the adverse event.

For livers that are not transplanted, the reason(s) for non-transplantation (including device failure) will be summarized using counts and percentages. The number and percentage of donor livers in the Donor Liver Population for which these was a device failure will also be presented.

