## 5.3. Other Endpoints

- Length of initial post-transplant ICU stay
- Length of initial post-transplant hospital stay
- Evidence of ischemic biliary complications diagnosed at 6 and at 12 months post-transplant
- Extent of reperfusion syndrome as assessed based on the rate of decrease of lactate over the following timepoints:
  - During anhepatic phase immediately before reperfusion of the transplanted liver
  - 30-40 minutes after hepatic artery and portal vein reperfusion of the transplanted liver
  - 90-120 minutes after reperfusion of the transplanted liver
- Pathology sample score for liver tissue samples taken at the following timepoints:
  - Donor liver pre-retrieval
  - Post-OCS preservation at the end of back preparation and immediately before the start of re-implantation
  - 90-120 minutes after reperfusion of the transplanted liver (prior to abdominal closure).

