#### **8.3.1. 6 and 12-Month Follow-up**

At approximately 6- and 12-months post-transplant, the patient will be evaluated at an office visit if this is the institution's standard of care, and, if not, by phone contact by the site. The patient's medical record may be reviewed to confirm patient's answers. This follow-up will collect information on:

- Patient and graft survival
- Liver graft-related SAEs (6 months only)
- Liver graft-related re-hospitalization after initial discharge, and, if yes, the primary reason/diagnosis for the hospitalization and the length of stay
- Information will also be collected on any diagnosis of ischemic biliary complications and, if so, the method of diagnosis and treatment.

The 6 and 12-month follow-up will be collected within  $\pm$  1 month of the designated period and will be recorded on the 6- and 12-month follow-up electronic form.

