## **9. EVALUATION OF ADVERSE EVENTS**

### **9.1. Evaluation of Liver Graft-Related Adverse Events (LGRAEs)**

Liver Graft-Related Adverse Events (LGRAEs) are those which have any untoward effect on the health or safety of the patient and that are related to the transplanted liver function (except for acute rejection). LGRAEs will be collected from the time a subject is transplanted with a liver preserved on OCS until the completion of the 30-day follow-up evaluation. A LGRAE will be followed until resolution or stabilization of the event.

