## APPENDIX 2. SCHEDULE OF CLINICAL ASSESSMENTS

Evaluations	
Eligibility & ID	X
Demographics/Characteristics	X
Donor Cause of Death	X
Donor Medical & Social History	X
Donor Liver Assessment	X
Donor Cross Clamp Time and Flush Detail	X
Post-Preservation Liver Biopsy and if applicable Bile duct specimen	X
OCS Preservation Parameters	X
OCS Liver Enzymes & Lactate Levels	X
Device Malfunction (if applicable)	X
Non-transplant Reasons (if applicable)	X

Evaluations	Recipient Schedule of Assessments					
	Tx. Day - Day 7 Post-Tx.	Discharge	Day 30	Month 6	Month 12	Month 24
Eligibility & Informed Consent	X					
Demographic/Characteristics	X					
Medical & Risk Factors	X					
Transplant Details	X					
Early Liver Allograft Dysfunction (EAD) Surveillance	X					
Mechanical Ventilator Support	X					
Patient Survival	X	X	X	X	X	X
Graft Survival	X	X	X	X	X	X
Immunosuppressive Meds & Induction (if applicable)	X	X				
Initial ICU & Hospital Stay	X	X				
Liver graft-related (AE's & SAE's)	X	X	X	X		
Liver graft-related re-hospitalizations				X	X	
Ischemic biliary complications				X	X	
Liver Biopsy *	X				X	X

\* ONLY tests regularly scheduled per center standard of care or performed due to a clinical cause at these timepoints will be collected.

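### The principal safety count closes at Day 30; later ischemic biliary complications are analysed primarily on Per Protocol, and no analysis is specified for the graft-related SAEs collected at 6 months

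*Combined protocol and SAP*

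**What the plan says.** Section 10.4, like section 5.4 and the synopsis, makes the principal safety analysis an "examination of the frequency of liver graft-related serious adverse events (SAEs) up to the 30-day follow-up after transplantation". The endpoint is a mean count per subject over four event types, with each type counted at most once per person. One of the four is "Ischemic biliary complications (ischemic biliary strictures, and non-anastomotic bile duct leaks").

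Section 5.3 lists among the Other endpoints: "Evidence of ischemic biliary complications diagnosed at 6 and at 12 months post-transplant". Section 10.2.1 assigns the analysis set: "The primary analysis of effectiveness and of secondary and other endpoints will be based on the PP Population". Section 10.2.2 puts the safety analysis on mITT, meaning everyone transplanted.

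For later follow-up, section 8.3.1 and the synopsis collect "Liver graft-related SAEs (6 months only"). Appendix 2 marks the row "Liver graft-related (AE's & SAE's") at Month 6 as well as at the earlier visits. Section 9.1, however, collects graft-related adverse events only "until the completion of the 30-day follow-up evaluation". Section 9.5 gives two further windows. One sentence stops capture at Day 30 or initial discharge, whichever is earlier; another extends recording to discharge when that falls after Day 30.

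After the principal endpoint, section 10.4 plans MedDRA tables of graft-related adverse events and adds "A similar analysis will be performed for LGRSAEs". No time window is given for these tables.

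**The concern.** Section 1.2 says the device is intended to reduce ischemia and reperfusion injury, and section 1.1 links ischemic injury to complications after transplant. The biliary type is the only component of the safety count named for ischemia. Because the protocol looks for it again at 6 and 12 months, the design allows for cases after the safety count has closed.

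Those later cases move out of the safety analysis and, for the primary analysis, into a narrower set defined partly by what happened after transplant. A report could then show a 30-day figure on all transplanted recipients and a late figure on a selected subset, with nothing stated to connect them. The SAEs gathered at 6 months, which could make the connection, have no assigned table. The conflicting collection windows also matter to sites, because they govern what is recorded; an analysis plan written later cannot recover events that were never entered.

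**Working it through.** The plan gives no figure to reproduce. Section 10.5 sets the maximum of 184 from the enrollment rate in the PROTECT trial, not from a power calculation. The check is therefore mainly a comparison of the text, with an illustration of scale.

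**Step 1. Treatment of the same harm before and after Day 30**

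| | To Day 30 | After Day 30 |
|---|---|---|
| Status | Part of the principal safety endpoint (5.4, 10.4) | Other endpoint (5.3) |
| Set for the primary analysis | mITT (10.2.2) | Per Protocol (10.2.1) |
| Method | Mean count per subject, one per type (10.4) | None given; 10.3 stops at the secondary endpoints |
| Counting rule | Cumulative from transplant | Diagnosed at each visit time; whether cumulative is not stated |

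**Step 2. Who differs between the sets.** mITT is all transplanted subjects. Per Protocol removes those whose donor liver did not receive the complete preservation procedure, those ineligible on recipient or donor criteria, those whose post-transplant assessments do not adequately support the primary, secondary or safety endpoints, and those with other major violations. The assessment criterion depends on information that arises after transplant.

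**Step 3. The 6-month SAEs.** Collection is stated in three places (synopsis, 8.3.1, Appendix 2). No endpoint in section 5 and no analysis in section 10 names that time point. The MedDRA tables could include these events, but their window is not stated. Section 9.1 and both windows in section 9.5 are tied to Day 30 or initial discharge, so none provides for collection at Month 6.

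**Step 4. Share of calendar time.** 30/182.6 = 16% of the period to 6 months; 30/365.25 = 8% of the period to 12 months. These are shares of days, not of risk.

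**Step 5. Illustration of scale.** The incidences and shares below are assumptions; the documents give neither. Subjects with a first biliary event outside the principal count = 184 × 12-month incidence × (1 − share diagnosed by Day 30).

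| Assumed 12-month incidence | Expected cases | Outside if 0% by Day 30 | 25% | 50% | 100% |
|---|---|---|---|---|---|
| 2% | 3.7 | 3.7 | 2.8 | 1.8 | 0 |
| 5% | 9.2 | 9.2 | 6.9 | 4.6 | 0 |
| 10% | 18.4 | 18.4 | 13.8 | 9.2 | 0 |

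**Step 6. What a clean 30-day result would show.** With no biliary events in 184 subjects, the exact two-sided 95% upper limit is 1 − 0.025^(1/184) = 2.0%. It bounds the 30-day risk only and says nothing about risk to 6 or 12 months.

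**The case against.** The strongest reply is that nothing has been lost. A 30-day principal endpoint is a legitimate choice in a single-arm continued access study with descriptive safety, late biliary complications are a pre-specified endpoint with data collected at both visits, and a separate SAP is still to come (10.3, 10.6). Much of this stands, and it rules out several stronger readings that a reader might infer:

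- *The 6-month SAEs enter no analysis, or every graft-related SAE table stops at Day 30.* Not supported. Only the principal endpoint carries the 30-day limit. The MedDRA tables have no stated window and could include later events.
- *A stricture diagnosed and treated at month 3 is lost.* Not supported as a matter of collection. Section 8.3.1 gathers information on any diagnosis, with method and treatment. The uncertainty lies in the wording of the endpoint in 5.3, which is narrower than the data.
- *The late analysis removes device failures.* Too broad. Under section 11.1, a subject whose donor liver is damaged by malfunction or error waits for another, so that case would not enter mITT through that liver either. Section 10.4 reports device failures separately on the Donor Liver Population. The sets differ on this ground only for recipients transplanted after incomplete preservation, and the documents do not say how many to expect.
- *The 30-day figure will look favourable mainly because the window closes early.* This rests on event timing that the documents do not give. The protocol also treats these complications as a 30-day event type.

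The reply does not remove the stated Per Protocol rule for Other endpoints, which is a decision already taken and not a detail awaiting the SAP. Nor does it remove the conflict over collection windows, which sits in the protocol and governs the sites.

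**Conclusion.** The point holds in a limited form. The primary form of the only named analysis of ischemic biliary complications after Day 30 is on a set that excludes some transplanted recipients, partly on post-transplant grounds, while the plan's own safety set is mITT. Section 10.2.1 makes Per Protocol the primary analysis, not the only one; but section 10.3, which names both sets for the primary and secondary endpoints, does not reach the Other endpoints. No analysis is specified for the graft-related SAEs collected at 6 months, and the collection windows disagree.

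The size cannot be fixed from the documents. Under the assumed incidences of 2% to 10%, between 0 and about 18 of 184 subjects would have a first biliary event outside the principal count. The lower end applies whenever every case is diagnosed by Day 30. The gap in the plan does not depend on these rates. It should be closed before the SAP is finalised, and it is no reason to abandon the 30-day endpoint.

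**What to change.** Keep the 30-day endpoint as it is, and make these changes:

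1. Add to section 10.4, on mITT, a descriptive summary of graft-related SAEs through 6 months, using the same four types and one per type per person. Primary non-function will not change, because it is defined within 10 days. State the time window of every safety table.
2. Add to section 10.4, on mITT, the cumulative proportion of subjects with any ischemic biliary complication diagnosed by 6 and by 12 months, resolved or not, with deaths and re-transplants reported alongside. Section 8.3.1 lists method of diagnosis and treatment but no diagnosis date, so competing-risk estimates should be planned only if dates are recorded. Simple proportions do not need them. As a guide to precision, 9 of 184 (4.9%) would have an exact 95% interval of 2.3% to 9.1%.
3. Reword the item in section 5.3, and its copy in the synopsis, so that complications are counted by 6 and by 12 months.
4. Reconcile sections 9.1 and 9.5 with the Month 6 collection in section 8.3.1 and Appendix 2, including the two windows within 9.5.

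The cost is wording and two descriptive tables from visits already planned. The small downside is that cumulative figures can only equal or exceed the 30-day ones, so the reported results may look less favourable.
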